Children with immunodeficiency, cystic fibrosis, acute or subacute symptoms, signs of bacterial infection, and/or those who are unable to cooperate with testing will be excluded. Children with documented use of the study medication in the month before evaluation and during period of symptoms will also be excluded.

Parents of the subjects will complete the SN-5 questionnaire as described below, at initial evaluation and again during a lead-in phase three days later to ensure stability of symptoms. Patients with an improved score will be excluded.

The Sinus and Nasal Quality of Life Survey (SN-5)

The Sinus and Nasal Quality of Life Survey (SN-5) is a validated and reliable questionnaire designed to score five areas of impact from sinonasal dysfunction (SN-5) in patients 1 year to 18 years of age^{9,10}. Parents assess the impact of infection on nasal symptoms, emotion, and activity on a scale of worsening symptoms scored 1 through 7 to provide a quantifiable score capable of comparing both disease severity and the impact of interventions on subjective complaints. It has been shown as a responsive measure of health-related quality of life

for children with persistent sinonasal symptoms, suitable for use in outcomes studies and routine clinical care. Kay et al showed SN-5 test-retest reliability with an R value of 0.70⁹. Terrell et al demonstrated that the SN-5 correlated to disease severity as measured by the Lung-MacKay CT scan score¹¹.

Acoustic rhinometry

Acoustic rhinometry is used to measure cross-sectional volume of the nasal cavity allowing the calculation of nasal volume. Audible reflected sound waves are painlessly introduced through nasal adaptors into the nasal passages allowing the production of area-distance graphs. As the acoustic rhinometer is calibrated to a standard nose, accurate results can be obtained with good test-retest reliability^{12,13}.

Analysis of nasal secretions

Secretion collection

Collection and analysis of nasal secretions will be performed under direct vision at the time of rhinologic assessment. These will be collected using the Jun-Tymp-Tap (Xomed, Jacksonville, FL) as previously described¹⁴.

Mucociliary clearability

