After informed consent is obtained, a medical history will be obtained, including demographic data of personal or family history of allergies, asthma, nasal or sinus disease, exposure to tobacco smoke, prior medication history and other associated conditions. A head and neck physical examination will be performed, including a thorough rhinoscopic examination. We will determine nasal patency both by direct visualization and scoring and by acoustic rhinometry pretreatment and at post treatment follow-up, using the mean of three consecutive measurements. Secretions will be collected from the middle meatus pre and post treatment using the Jun-Tym-Tap. The SN-5 questionnaire will be completed at two baseline visits and after completion of the study.

The subject will be given a 14- day course of either guaifenesin or matched placebo to be taken orally three times daily according to following age-matched dosages: children aged 7-11 years old will receive guaifenesin 200 mg TID, while children older than 12 will receive guaifenesin 400 mg TID. Randomization of medication use will be carried out by a study participant not involved in the direct care of the patient. A 2:1 ratio of subjects on active medication to placebo will be used. After two weeks, the subject will return for data collection including nasal examination, SN-5, acoustic rhinometry, and collection of nasal secretions. Subjects that do not return for their follow up visit will be contacted to schedule repeat examination.

Data Analysis

Power calculation

The primary outcome variable will be changes in the SN-5 questionnaire score. It has been reported that the mean score in children with CRS is 3.8 with a standard deviation of 1.0 and a temporal effect size of standard therapy equal to 0.88¹¹. Thus assuming a normal distribution of results, using a paired 2-tail test to evaluate pre and post treatment outcome with an α error probability of 0.05 and a β (power) to detect a change of 0.88 at 80%, the critical t is 2.1788 yielding a sample size of 13 subjects per group¹⁷.

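### The SN-5 comparison with placebo would be more precise if the protocol stated a baseline-adjusted model and said how the two baseline scores are used

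*Protocol*

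**What the plan says.** The Power calculation paragraph under Data Analysis states that "The primary outcome variable will be changes in the SN-5 questionnaire score". The sample size is then derived "using a paired 2-tail test to evaluate pre and post treatment outcome", from the figures that "the mean score in children with CRS is 3.8 with a standard deviation of 1.0" and a before-after effect size of 0.88. The Study Protocol section adds that "The SN-5 questionnaire will be completed at two baseline visits and after completion of the study".

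Under Subject Recruitment, the second baseline score is taken "again during a lead-in phase three days later to ensure stability of symptoms", and "Patients with an improved score will be excluded". That is the only use given for the second score. The protocol does not say whether change is measured from the first score, the second score or their mean.

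Hypothesis 1, at the end of the Introduction, sets guaifenesin against placebo. With 36 children at 2:1, that means 24 v 12. No model for this comparison is given, with or without a baseline covariate.

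**The concern.** A change score subtracts the whole baseline value, including its measurement error. A model with baseline as a covariate subtracts only the part that predicts the final score. It also corrects for chance baseline differences between the arms, which can be appreciable when one arm has 12 children. The protocol cites a test-retest R of 0.70 for the SN-5, so a single baseline score carries a good deal of noise.

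The second baseline score is already collected, and averaging the two reduces that noise. If it serves only as a screen, the information is paid for but not used. What is at stake is the width of the confidence interval for active minus placebo, not the validity of the comparison.

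**Working it through.** **The plan's own figure.** A paired two-sided t test at 0.05 with standardised effect 0.88 has power 79.2% at n = 12 and 82.9% at n = 13. At n = 13 the critical t is 2.1788 (12 df). The stated 13 per group and critical t therefore reproduce. The calculation contains no between-arm comparison, so baseline adjustment does not alter it.

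**Inputs for the placebo comparison.**
- SD 1.0 at each time (Power calculation).
- 24 v 12 (36 at 2:1).
- Correlation between the two baselines 0.70, the stated test-retest value.
- Correlation r of each baseline with the 14-day score: not in the protocol. It is assumed to be 0.70 or 0.50.

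**Mechanism, before any lead-in selection, with one baseline.** Per-child variance is 2(1 - r) for a change score and 1 - r² for the adjusted analysis. The ratio is (1 + r)/2.
- r = 0.70: 0.60 v 0.51, ratio 0.85.
- r = 0.50: 1.00 v 0.75, ratio 0.75.

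The adjusted analysis has the smaller variance whenever r is below 1.

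**With the lead-in exclusion.** Removing improvers restricts the joint distribution of the two baselines, so the closed forms no longer apply exactly. Trials were simulated from a trivariate normal distribution. Only children whose second score was not better than the first were kept, and the 24 v 12 comparison was made in each trial. The simulated SEs already include the cost of estimating the baseline slope.

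| r | SE, change from one baseline | SE, adjusted for mean of two | Variance removed |
|---|---|---|---|
| 0.70 | 0.250-0.251 | 0.233 | 1 - (0.233/0.250)² = 13.1% to 1 - (0.233/0.251)² = 13.8% |
| 0.50 | 0.336-0.339 | 0.303 | 1 - (0.303/0.336)² = 18.7% to 1 - (0.303/0.339)² = 20.1% |

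In equivalent sample size this is 1/0.869 = 1.15 to 1/0.862 = 1.16 times the children at r = 0.70. At r = 0.50 it is 1/0.813 = 1.23 to 1/0.799 = 1.25 times.

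**How much is due to adjustment itself.** A change score can also be taken from the mean of the two baselines, so that is the like-for-like comparator.
- r = 0.70: SE 0.238 for change from the mean v 0.234 adjusted (a separate run, so it differs from the table in the third decimal). 1 - (0.234/0.238)² is about 3%. Averaging supplies most of the 13-14%.
- r = 0.50: about 14% less variance from adjustment beyond averaging.

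Repeat runs of 20,000 trials per setting mostly moved these percentages by a point or less.

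**The case against.** The strongest reply is that the protocol never commits to an unadjusted comparison. It names change as the outcome variable, and that does not exclude a covariate: a linear model of change from a given baseline, adjusted for that baseline, gives the same arm effect as a model of the final score with the same covariate. The SAP is not shown, and the choice of covariate often sits there. This stands. A reader might infer that the protocol prescribes a raw, unadjusted change-score test against placebo. The text does not support that, so the loss is conditional on how the comparison is eventually made.

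A reader might also infer a larger gain. Without lead-in selection, change from one baseline has variance 0.60 and adjustment for the mean of two has 1 - 0.70²/0.85 = 0.42, a drop of about 29%. That figure should not be used. It credits adjustment with what averaging does: on equal terms the variances are 0.45 and 0.42. It also describes children whom the lead-in rule would partly exclude. Smallest detectable differences worked out on the same basis fail for the same reasons.

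Finally, the mismatch between a within-group paired test and a hypothesis about placebo is the larger issue in this paragraph. That is a separate point. It does not remove this one, because settling the between-arm analysis requires stating the baseline and the covariate.

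**Conclusion.** The point holds as an efficiency improvement, not as an error. Where the protocol speaks about analysis, it describes change and a paired pre/post test. It names no covariate and leaves the baseline undefined although two scores are taken. For the 24 v 12 comparison, adjusting for the mean of both baselines removes about 13-14% of the variance relative to change from a single baseline at r = 0.70, and about 19-20% at r = 0.50. Adjustment beyond averaging contributes about 3% and about 14% respectively.

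These sizes rest on normal scores, SD 1.0, a baseline-to-baseline correlation of 0.70, literal exclusion of improvers, and an assumed baseline-final correlation. The value 0.70 is a test-retest figure, and the correlation across 14 days of treatment could differ. No gain is quantified for rhinometry, % obstruction or the mucus measures, because the protocol gives no pre/post correlation for any of them.

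**What to change.** In the Data Analysis section, state the primary analysis in one sentence: SN-5 after treatment (or, equivalently, its change from the mean of the two pre-treatment scores) is compared between arms in a linear model with arm and that mean as covariate, and the adjusted active-minus-placebo difference is reported with its 95% CI. This also settles which baseline defines the change.

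The cost is one residual degree of freedom (36 - 2 = 34 becomes 33) and a line of text. No extra children, visits or questionnaires are needed.

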In this pilot study we will test the hypothesis that:

- 1) Guaifenesin use over a period of 14 days improves subjective nasal complaints in pediatric patients with chronic rhinitis and nasal congestion, as measured by the SN-5 survey compared to use of placebo.
- 2) There will be an observed improvement in nasal volume and cross-sectional area following use of guaifenesin, measured objectively using acoustic rhinometry compared to use of placebo.
- 3) Following treatment with guaifenesin, nasal secretions will have more favorable mucociliary and sneeze clearability compared to use of placebo.
- 4.) Children that respond and those that do not respond to guaifenesin therapy will show significant differences in mucus characteristics and mucociliary clearance.

Materials and Methods

Study Design

This is a 14-day, randomized, placebo-controlled, parallel group, masked clinical trial of oral guaifenesin for the therapy of CRS in 36 children between the ages of 7 and 18 years. A 2:1 ratio of subjects on active medication to placebo will be used. Before starting the study, this study will be approved by the Virginia Commonwealth University Institutional Review Board for human research. Study subjects will be assigned a unique coded identifier and all information will be entered into an Excel database in a password-protected computer, to which only the investigators have access. There is minimal risk to the child in acoustic rhinometry measurements, collecting nasal secretions, and completing the SN-5 surveys.

Subject Recruitment

We will enroll 36 subjects from the pediatric otolaryngology clinic at the Virginia Commonwealth University Medical Center in a 2:1 ratio of active medication to placebo. The subjects will be between the ages of 7 and 18 years at the time of the study. They will be identified during routine clinical evaluation for CRS as defined as chronic rhinitis and nasal stuffiness of at least 3 months duration. Informed consent will be obtained from the subject's parent or legal guardian and assent will be obtained from the study subjects. Given our clinic volume we anticipate that it will take 12 months to complete subject enrollment.

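### The 80% power and 13 per group come from a one-arm before/after test; at the same effect size, 36 children at 2:1 give about 68% power against placebo

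*Protocol*

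**What the plan says.** Under Study Design the protocol states: "This is a 14-day, randomized, placebo-controlled, parallel group, masked clinical trial of oral guaifenesin". The size is given in the same place as "oral guaifenesin for the therapy of CRS in 36 children between the ages of 7 and 18 years", and allocation as "A 2:1 ratio of subjects on active medication to placebo will be used". The first hypothesis in the Introduction is that 14 days of guaifenesin improves nasal complaints, "as measured by the SN-5 survey compared to use of placebo".

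Under Data Analysis, Power calculation: "The primary outcome variable will be changes in the SN-5 questionnaire score". The inputs are a mean score of 3.8, a standard deviation of 1.0 and an effect size of 0.88, which the protocol describes as temporal and attributes to standard therapy. The calculation is made "using a paired 2-tail test to evaluate pre and post treatment outcome", "with an α error probability of 0.05" and 80% power, and concludes that "the critical t is 2.1788 yielding a sample size of 13 subjects per group".

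The protocol gives no power for the comparison with placebo, no step from 13 per group to 36 at 2:1, and no allowance for children who do not return.

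**The concern.** The test that was sized is not the test of the hypothesis. A paired pre/post test asks whether one arm changes from baseline. Natural improvement, regression to the mean or a placebo response can all make it positive, so it cannot show superiority to placebo. Expressing the result per group invites the reader to take it as a two-arm calculation.

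The sample size also fails the protocol's own requirement, since 2:1 allocation of 36 leaves fewer than 13 on placebo.

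At stake is how the result is read. The protocol says these pilot data will be used to develop a further controlled study. A null comparison with placebo could be taken as coming from a trial with 80% power, and the next study could be planned on that footing.

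**Working it through.** **Inputs from the protocol.** Two-sided α = 0.05; power 80%; effect 0.88; score SD 1.0; critical t 2.1788; 13 per group; N = 36 at 2:1, so 36 × 2/3 = 24 on drug and 36 × 1/3 = 12 on placebo. The SD of the change is not stated.

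**1. Reproducing the protocol's figure.** For a paired t test, df = n − 1 and the noncentrality is 0.88 × √n.

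| n | df | critical t | power |
|---|---|---|---|
| 12 | 11 | 2.2010 | 79.2% |
| 13 | 12 | 2.1788 | 82.9% |

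Thirteen is the smallest n reaching 80%, and the critical t matches to four decimals. A two-sample test would have df = 24 (13 v 13) or df = 34 (24 v 12). The stated figure is therefore a single-group calculation with a standardized change of 0.88.

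**2. The comparison with placebo, same effect size.** For a two-sample t test, df = 24 + 12 − 2 = 34, critical t = 2.032, and the noncentrality is d × √(24 × 12/36) = d × √8.

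- d = 0.88: noncentrality 0.88 × 2.828 = 2.489; power **67.7%**.
- 80% power at 24:12 requires d of about **1.02**.
- At 2:1, 80% power for d = 0.88 is first reached at 32:16, or 48 children (80.3%); 30:15 gives 77.6%.
- Two arms of exactly 13 would give 57.7%.

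**3. If some of the 0.88 is change that placebo children also show.** The fractions are assumptions chosen to show the range.

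- A quarter removed, d = 0.75 × 0.88 = 0.66: power 44%.
- Half removed, d = 0.50 × 0.88 = 0.44: power 23%.

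**4. Alternative reading: 0.88 in SN-5 points.** With score SD 1.0 at both times and pre/post correlation r, the SD of change is √(2(1 − r)) and the residual SD after baseline adjustment is √(1 − r²). At r = 0.70 these are 0.775 and 0.714. The correlation is an assumption: the only such figure in the protocol is the SN-5 test-retest value of 0.70, which is not a correlation across treatment. Power at 24:12, with df kept at 34:

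| r (assumed) | placebo change | change score | baseline-adjusted |
|---|---|---|---|
| 0.3 | none | 53% | 72% |
| 0.5 | none | 68% | 80% |
| 0.7 | none | 88% | 92% |
| 0.7 | 0.30 points | 54% | 61% |

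The last row uses a net difference of 0.88 − 0.30 = 0.58 points; the 0.30 is an assumption.

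**The case against.** The protocol's arithmetic is correct, and it attaches the 80% openly to a paired pre/post test. It never claims 80% for the placebo comparison, and per group could mean a paired test within each arm. That is a fair account of where the number comes from. It does not help the plan: the hypothesis is comparative, this is the only sample-size justification offered, and it does not address that hypothesis.

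The 68% is conditional. The protocol gives no SD of change and calls 0.88 both an effect size and a change, so on the points reading between-arm power could exceed 80%. This stands as a limit on the figure. Like for like, however, 13 follows only if 0.88 is already standardized by the SD of change, and the higher figures need a favourable correlation and no improvement on placebo.

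The shortfall of 12 against 13 is small in itself: 79.2% against the 80% target on the paired test. That also stands; the point is an internal inconsistency with no margin for loss, and is secondary to the wrong test.

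The protocol does not say whether the source of 0.88 had a control group, so one can say only that it is not shown to be net of placebo change.

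Finally, this is a pilot and need not have 80% power. True, but it states a power target and a placebo-controlled hypothesis, so the two should agree. How a null result would be read is a judgement, not something the protocol states.

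**Conclusion.** The concern holds. The stated 80% power and 13 per group belong to a one-arm paired test, the first hypothesis is a comparison with placebo, and no power is given for that comparison. These points, and the 12 on placebo against a stated need of 13, follow from the protocol without further assumptions.

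The size of the shortfall does rest on an assumption. With 0.88 as the standardized between-arm difference in change and full follow-up of all 36, power is about 68% instead of 80%. Any placebo improvement or loss to follow-up lowers it; a strong baseline correlation with adjustment raises it. Because the error affects the only sample-size justification for the primary outcome, it should be corrected.

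**What to change.** Keep 36 children and rewrite the Power calculation paragraph:

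- Name the between-arm comparison of SN-5 change as the primary analysis, so that the power statement refers to a test the protocol specifies.
- State that 24:12 gives about 68% power for a standardized between-arm difference in change of 0.88, and 80% power for about 1.02, at two-sided 0.05.
- Remove 13 per group as the justification for the sample size.
- Say that 0.88 is a before/after effect of standard therapy and is not known to be net of placebo change.
- If a baseline-adjusted analysis is adopted, give its power with the assumed baseline/follow-up correlation shown.

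The cost is one paragraph and a less favourable power figure. No extra children are needed. Restoring 80% at 0.88 with the unadjusted test would take 48 − 36 = 12 more children at 2:1, which this fix does not ask for.

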We will also compare pre and post treatment nasal patency scores based upon subjective direct visualization score of % obstruction by a single investigator and objective mean acoustic rhinometry values, and pre- and post treatment mucus biophysical properties. Collected data will be used to evaluate the outcome measures most predictive of therapeutic response. We will compare responders to non-responders to see if there are factors in the history, physical examination, demographics (e.g. tobacco smoke exposure), or baseline measurement that predict response to guaifenesin. These pilot data will be used to develop a focused controlled prospective study of children and adults most likely to respond to oral guaifenesin.

References

- 3.) Bailey BJ and JT Johnson. Head & Neck Surgery – Otolaryngology: Fourth Edition. Lippincott Williams & Wilkins. 2006:vol 1, 405-416.

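### Hypotheses 2 and 3 are stated against placebo, but the only comparison the protocol names for their measures is pre versus post treatment

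*Protocol*

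**What the plan says.** The Study Design section describes the trial in these words: "This is a 14-day, randomized, placebo-controlled, parallel group, masked clinical trial of oral guaifenesin". It plans 36 children "in a 2:1 ratio of active medication to placebo", so 24 and 12.

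The hypotheses follow that design. Hypothesis 2 expects better nasal volume and cross-sectional area, "measured objectively using acoustic rhinometry compared to use of placebo". Hypothesis 3 expects that "nasal secretions will have more favorable mucociliary and sneeze clearability compared to use of placebo".

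The Data Analysis section does not carry the comparator through. Its power calculation, for the primary SN-5 outcome, is based on "using a paired 2-tail test to evaluate pre and post treatment outcome". The next paragraph turns to the other outcomes: "We will also compare pre and post treatment nasal patency scores based upon subjective direct visualization score of % obstruction by a single investigator", and then "objective mean acoustic rhinometry values, and pre- and post treatment mucus biophysical properties". The section never mentions placebo. The only contrast between groups of children that it names is responders against non-responders, and those are not the randomised arms.

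**The concern.** A within-child change mixes any drug effect with everything else that can move between the two visits: the natural course of the condition, regression towards the mean in children identified while being evaluated for symptoms, and, for a subjective score, the assessor's expectation of improvement. The randomised placebo arm is what separates these from the drug. A comparison of pre with post leaves it out.

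The three-day lead-in gives little protection here. It screens on the SN-5 alone and does not touch rhinometry or mucus.

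The visual % obstruction score is more exposed than the instrumental measures, because it is subjective and given by a single investigator. Masking conceals the arm but does not by itself conceal whether a visit is before or after treatment.

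At stake is a before-and-after improvement on guaifenesin being taken as support for hypothesis 2 or 3. The protocol says that these pilot data will shape a later controlled study, so a false signal would carry forward.

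**Working it through.** **1. Hypothesis and stated comparison, side by side**

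| Measure | Comparator in the hypotheses | Comparison in Data Analysis |
|---|---|---|
| Rhinometry volume and area | Placebo (hypothesis 2) | Pre v post |
| Mucus properties, including clearability | Placebo (hypothesis 3) | Pre v post |
| Visual % obstruction | None; no numbered hypothesis | Pre v post |

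The first two rows conflict. In the third row the conflict is with the placebo-controlled design, not with a hypothesis.

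**2. What the protocol's own test is**

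The protocol gives no figure for the secondary outcomes. For the SN-5 it gives effect size 0.88, two-sided alpha 0.05, 80% power, critical t 2.1788 and 13 per group. For a paired t-test on n children, df = n − 1, the noncentrality is d√n, and power comes from the noncentral t distribution.

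- n = 13: df = 12, critical t = 2.1788, power 82.9%.
- n = 12: power 79.2%.

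The stated 13 reproduces. The one test that Data Analysis names is therefore a test of change within a group, with no placebo term.

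**3. What the same kind of test would do to the secondary outcomes with no drug effect**

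Inputs: 36 children at 2:1 gives 36 × 2/3 = 24 active and 36 × 1/3 = 12 placebo; two-sided alpha 0.05. Assumption: both arms change equally for non-drug reasons by d = 0.25, 0.5 or 0.75 SD of the change score. The protocol gives no value for d, so this is a range.

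Critical t is 2.069 (df 23) for the active arm and 2.201 (df 11) for placebo. The noncentrality is d√24 = 1.22, 2.45, 3.67 and d√12 = 0.87, 1.73, 2.60.

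The arms are independent, so P(significant on drug, not on placebo) = P(active significant) × [1 − P(placebo significant)].

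| d | Active significant | Placebo significant | Active yes, placebo no |
|---|---|---|---|
| 0.25 | 21.7% | 12.4% | 0.217 × 0.876 = 19% |
| 0.5 | 65.0% | 35.3% | 0.650 × 0.647 = 42% |
| 0.75 | 94.0% | 65.8% | 0.940 × 0.342 = 32% |

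Over all values of d, the last column peaks at about 43%, near d = 0.55. A valid two-sided comparison of the arms would be significant 5% of the time in each row, because the true difference is zero.

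**4. What the between-arm comparison can detect**

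For an unadjusted two-sample t-test with 24 and 12, df = 34, critical t = 2.032 and the noncentrality is δ√(24 × 12/36) = δ√8. Power is 80% at δ = 1.02 SD. Borrowing the SN-5 figure of 0.88 as an assumption gives power of 67.7%. Both are before any gain from baseline adjustment.

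**The case against.** The strongest reply is that the sentence names no test and does not say that placebo is ignored. In a parallel-group trial, pre and post may simply be the measurements from which change is derived, to be compared between arms as the hypotheses require. The paired test sits under Power calculation and concerns the SN-5; the word 'also' adds outcomes and need not carry that test over to them. How change is contrasted is commonly left to a SAP, and none is shown.

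Part of this stands. The choice of model can be left to a SAP, and the calculation in step 3 is conditional: the protocol does not say that paired tests will be run separately in each arm for these outcomes. But the between-arm reading is written nowhere in Data Analysis, and the one test that is written there is within-group. The protocol has not left the comparison open; it has named one that differs from its hypotheses, and a SAP written faithfully to it would inherit the mismatch.

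Four stronger readings are tempting, and the documents do not support them:

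- **That the trial cannot test hypotheses 2 and 3, or discards its placebo data.** Study Protocol takes these measurements before and after treatment without restricting them to the active arm. The limit is in the stated analysis only.
- **That % obstruction fails to test hypothesis 2 or 3.** It belongs to neither.
- **That assessor expectation undermines all three sets of measures.** It bears on the visual score and hardly on rhinometry or rheology, which are instrumental.
- **That 2:1 allocation makes significance on drug but not on placebo likely.** The chance never exceeds about 43%. It is well above 5%, but not more likely than not.

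**Conclusion.** The point holds for the analysis as written. For rhinometry and mucus properties, the stated pre/post comparison does not answer hypotheses framed against placebo. For the visual score, it leaves the design's control unused on the outcome most open to assessor expectation.

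The size depends on an assumed non-drug change, equal in the two arms, and on paired tests being run within each arm. Under those assumptions, a null drug would look active in the guaifenesin arm in roughly one trial in five (0.25 SD) to more than nine in ten (0.75 SD). The misleading split between arms would appear in 19% to 42% of trials at the three values tried.

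The SN-5 shows the same mismatch between a placebo hypothesis and a paired calculation. Correcting only the SN-5 sample size would leave the present point standing.

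This is a should-fix: the outcomes are secondary, the study is a pilot, and the remedy is wording.

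**What to change.** Replace the sentence in Data Analysis on nasal patency, rhinometry and mucus properties with:

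*For acoustic rhinometry, each mucus property and % obstruction, the post-treatment value will be compared between guaifenesin and placebo, adjusted for the child's baseline value, with a 95% confidence interval; within-arm pre/post changes are descriptive only.*

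A between-arm comparison of change would also answer the hypotheses; baseline adjustment is preferred because it usually gives a tighter estimate.

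No new patients or measurements are needed. The cost is precision: an interval for a difference between 24 and 12 children is wider than one for change within an arm, and only differences of about 1 SD are detectable with 80% power before adjustment.

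### The search for factors that predict response to guaifenesin gives the placebo arm no role, so it may not separate drug-specific predictors from markers of natural course

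*Protocol*

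**What the plan says.** The protocol's Data Analysis section ends with an exploratory aim: "We will compare responders to non-responders to see if there are factors in the history, physical examination", demographics "or baseline measurement that predict response to guaifenesin". The use of the result follows: "These pilot data will be used to develop a focused controlled prospective study of children and adults most likely to respond to oral guaifenesin".

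Hypothesis 4 rests on the same split: "Children that respond and those that do not respond to guaifenesin therapy will show significant differences in mucus characteristics" and in mucociliary clearance. It is the only one of the four hypotheses without a placebo comparison. Hypothesis 3, for example, says "nasal secretions will have more favorable mucociliary and sneeze clearability compared to use of placebo", and hypotheses 1 and 2 carry the same reference.

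A placebo arm is available. Study Design plans 36 children, and "A 2:1 ratio of subjects on active medication to placebo will be used", which gives 24 active and 12 placebo. The Study Protocol section applies the same history, examination, and pre- and post-treatment measurements to both arms.

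**The concern.** Response is judged from one before-and-after course per child. Among treated children, improvement on the SN-5 mixes drug effect, natural course, placebo response and measurement error. A factor associated with improvement there may be purely prognostic: children who carry it would have improved on placebo too. Pooling the arms does not help, because the factor works in both arms and 36 children detect it more often than 24. Baseline SN-5 is a special case, since a high baseline score partly reflects error and tends to fall on re-measurement.

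The protocol names the conclusion (prediction of response to guaifenesin) and its use (choice of the next population). If a prognostic factor is read as a predictor, the next study leans towards children who improve anyway.

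**Working it through.** **The plan's own figure.** The only sample-size figure in Data Analysis is 13 per group, from a paired two-sided t-test with effect size 0.88. With df = n − 1 and noncentrality 0.88·√n, n = 13 gives critical t 2.1788 and power 82.9%; n = 12 gives 79.2%. The figure reproduces. It is a within-group pre/post calculation and does not bear on the responder comparison.

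**Inputs from the protocol.** 24 active and 12 placebo; SN-5 mean 3.8, SD 1.0; test-retest R 0.70; the lead-in rule "Patients with an improved score will be excluded".

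**Assumed, not in the protocol.** Responder cut of 0.5 points; a yes/no factor carried by 30–50% of children; prognostic effects of 0.25, 0.5 and 0.88 points; Fisher's exact test at 5%; baseline taken as the first score, the second, or their mean. The protocol gives 0.88 as a therapy effect, so as a prognostic effect it is only an upper illustration.

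**Model.** Each score is a true score (variance 0.70) plus error (variance 0.30). A child is kept only if the second baseline score is not lower than the first. The drug is inert. The factor lowers the 14-day score equally in both arms, so every flag is a false claim of drug-specific prediction.

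| Prognostic effect | 24 active | 36 pooled |
|---|---|---|
| none | 1–3% | 2–4% |
| 0.25 points | 4–6% | 6–10% |
| 0.5 points | 13–22% | 22–34% |
| 0.88 points | 39–59% | 63–82% |

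The ranges cover prevalence, baseline choice and, for 0.5 points, repeated runs. The arm-by-factor test stays at 4–6% throughout.

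**Sensitivity to the cut** (24 active, 0.5 points): 11–22% at a cut of 0.25 and 2–15% at a cut of 1.0.

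**A simpler model** (change scores with SD 1, half of each arm carrying the factor, cut 0.5 SD) gives 9% active and 15% pooled for a 0.5 SD factor, and 28% and 46% for 0.88 SD. The interaction test stays near 5%. The pattern is the same and the level is lower.

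**Baseline SN-5 as the factor** (t-test by responder status, cut 0.5): flagged in 13–20% of testable trials in 24 active children and 18–29% pooled, through regression to the mean. The arm-by-baseline test stays at about 5%.

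**Precision of the interaction.** For prevalence p,

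SE = SD × √[1/(24p) + 1/(24(1−p)) + 1/(12p) + 1/(12(1−p))], df 31, t ≈ 2.04.

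- p = 0.5, SD 0.775 (= √(2 × 0.30)): 0.775 × √(1/12 + 1/12 + 1/6 + 1/6) = 0.548. The 95% CI half-width is 1.12 points and power for 0.88 points is 34%.
- p = 0.3, SD 1.0: √(1/7.2 + 1/16.8 + 1/3.6 + 1/8.4) = 0.772. The half-width is 1.57 points and power is 20%.
- Over this range, 80% power needs an interaction of 1.6–2.2 points.

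**The reverse error.** A purely drug-specific 0.88-point factor was flagged in the active arm with a non-significant interaction in 23–28% of simulated trials.

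**The case against.** The strongest reply is that this is silence rather than error. The paragraph is one exploratory statement that names no population, cut-off or test. Nothing in it forbids comparing responders with non-responders in each arm and then setting the arms side by side, and an SAP could say so. That stands in part: the wording permits a sound reading, so it would be wrong to infer that every reading fails. But the missing piece is more than a cut-off or a test. The protocol itself ties this contrast to a drug-specific conclusion, and no choice of cut-off makes a one-arm or pooled contrast support it.

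A reader might also infer that the protocol ignores placebo altogether. It does not: hypotheses 1 to 3 use it. The gap is confined to the responder comparison and hypothesis 4.

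The size rests on assumed inputs, and that objection stands. No passage supports a 0.5-point natural-course effect over 14 days in children with at least three months of symptoms, and the rates move with the cut.

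Finally, with an inert drug the main comparison would usually show nothing. In simulation, a 0.5-point factor was flagged and the between-arm SN-5 comparison also significantly favoured guaifenesin in only 0.2–0.5% of trials. That limits the harm in this setting. However, the protocol does not make the search for predictors conditional on a positive result. And if the drug helped all children equally, a prognostic factor would still separate responders from non-responders in the active arm.

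**Conclusion.** The point holds, at minor severity. As worded, the responder comparison can be run within the active arm or pooled, and then it cannot tell a predictor of drug effect from a marker of natural course or regression to the mean. With an inert drug, SD 1.0, R 0.70, an assumed cut of 0.5 and an assumed prevalence of 30–50%, a 0.5-point prognostic factor is flagged in about 13–22% (24 active) or 22–34% (pooled) of trials, against about 5% for the arm-by-factor test. At 0.25 points there is little harm.

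A reader might infer that the trial's efficacy conclusion is at risk. The documents do not support that: the aim is exploratory, the primary SN-5 comparison does not depend on it, and the next study is to be controlled. The cost is a poorly chosen population and lost efficiency.

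It is also tempting to call every association seen in only one arm prognostic. That goes too far the other way. An association in the active arm alone is also what a true predictor produces, and at 24:12 the interaction test misses most of these.

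**What to change.** In the last paragraph of Data Analysis, keep the responder comparison as descriptive, show each factor's association with SN-5 change in both arms, and add:

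> Any statement that a factor predicts response to guaifenesin will rest on the arm × factor interaction in all randomized children with 14-day SN-5 data (14-day SN-5 on baseline SN-5, arm, factor, arm × factor; for baseline SN-5 itself: baseline, arm, arm × baseline), reported with its 95% CI as hypothesis-generating. Other factors will be described as associated with improvement, with their drug-specificity undetermined.

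For hypothesis 4, show the link between mucus properties and response in both arms and describe it as an association.

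The change is wording only, since the data are already collected in both arms. The price is low precision: a 95% CI of about ±1.1 to 1.6 SN-5 points, and 20–34% power for a 0.88-point interaction under the assumed SD of 0.775–1.0. At 30% prevalence only about 12 × 0.3 = 3.6 placebo children carry the factor, and in 0.7^12 = 1.4% of trials none would, so the interaction could not be estimated. Multiplicity remains: ten independent tests at 5% give 1 − 0.95^10 = 40% chance of at least one false positive, hence the hypothesis-generating label. Few predictors could be claimed.
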